## 9.9 Age at Time of an Event

If age at the time of an Event is derived, the following algorithm will be used for the derivation

- Year of event minus year of birth

## 9.10 Laboratory Toxicity grading

In NCI-CTCAE v5.0 (see Section 18.1) the following parameters are not gradable at baseline as grading implies dependencies to baseline (e.g. ALT grade 1: >ULN - 3.0 x ULN if baseline was normal; 1.5 - 3.0 x baseline if baseline was abnormal):

- Eosinophilia (added term, grade 1 depends on baseline)
- Alanine aminotransferase increased
- Alkaline phosphatase increased
- Aspartate aminotransferase increased
- Blood total bilirubin increased
- Creatinine increased
- GGT increased
- INR increased (dependent on baseline also in v4.03)

In addition, in v5.0 the term 'Hyperglycemia' does not depend on glucose laboratory measurements anymore and is thus excluded from laboratory analyses and part of AE reporting only.

For the term 'Hemoglobin increased' the dependency to baseline is removed in v5.0. 'INR increased' is dependent on baseline values and intake of anticoagulants in both versions.

## 10 Study Participants

The subsections in this section include specifications for reporting participant disposition and study intervention/study discontinuations. Additionally, procedures for reporting protocol deviations are provided.

### 10.1 Disposition of Participants and Discontinuations

The number and percentage of participants in each of the below disposition categories will be presented as indicated in section 9. Percentages will be presented with respect to the number of participants in FAS/SAF analysis set.

Participant disposition will be summarized as follows:

- Number of participants in each analysis population (SCR, FAS/SAF, DLT, PKAS, Pd)
- Number of participants who discontinued from the study prior to study intervention overall and grouped by the main reason for discontinuation:
  - Participant did not meet all eligibility criteria
  - Withdrew consent
  - Other (COVID-19-related and COVID-19-non-related)

The end of study intervention status will be summarized by:

- Number of participants who received at least one dose of study intervention
- Number and percentage of treated participants with ongoing study intervention
- Number and percentage of treated participants who completed study intervention (overall and by reason):
  - Death
  - Progressive disease
- Number and percentage of treated participants who discontinued the study intervention (overall and by primary reason):
  - Adverse event
  - Lost to follow-up
  - Protocol non-compliance
  - Death
  - Withdrew consent
  - Other (COVID-19-related and COVID-19-non-related)

This table will be produced twice if there are participants with differing planned dose and actual dose, one by planned dose and one by actual dose.

The end of study status will be summarized by:

- Number and percentage of participants with ongoing study intervention
- Number and percentage of participants off-treatment and in follow-up
- Number and percentage of participants who completed the study (overall and by primary reason):
  - Progressive disease
  - Death
- Number and percentage of participants who prematurely discontinued the study (overall and by primary reason)

- Adverse event
- Lost to follow-up
- Protocol non-compliance
- Death
- Progressive disease
- Withdrew consent
- Other (COVID-19-related and COVID-19-non-related)

Additionally, the number of participants screened, and enrolled in each analysis set (SCR, FAS/SAF, DLT, PK and Pd) will be provided overall by region, by country within region and by site.

Disposition of participants by allocated study intervention dose will be presented in a CONSORT Flow Diagram.

## **10.2 Protocol Deviations / Exclusion from Analysis Sets**

### **10.2.1 Important Protocol Deviations**

Important protocol deviations (IPDs) are protocol deviations that might significantly affect the completeness, accuracy, and/or reliability of the study data or that might significantly affect a participant's rights, safety, or well-being.

Important protocol deviations include:

- Participants enrolled and dosed on the study who did not satisfy enrolment criteria
- Participants that develop withdrawal criteria whilst on the study but are not withdrawn
- Participants that receive an incorrect dose
- Participants that receive a prohibited concomitant medication
- Failure to collect data necessary to interpret primary endpoints
- Failure to collect necessary key safety data
- Deviation from Good Clinical Practice (GCP)
- Any other protocol deviation that might significantly affect the completeness, accuracy, and/or reliability of the study data or that might significantly affect a participant's rights, safety, or well-being.

Important protocol deviations will be identified for all participants by either site monitoring, medical review processes or programming and confirmed prior to or at the Data Review Meeting at the latest. Any important protocol deviations are documented in SDTM datasets whether identified through site monitoring, medical review processes or programming. The management of protocol deviations is outside of this IAP document.

Clinically important protocol deviations (CIPDs) are a subset of important protocol deviations that could impact the key objectives of the study and that would lead to the exclusion of a participant from an analysis set (see Section 8.1 Definition of Analysis Sets).

CIPDs may be identified during the course of the study but will not require amendments to this IAP.

Important protocol deviations or important events that might have an effect on PK include, but may not be limited to the following:

- Adverse events, diarrhea etc. (these instances will be discussed on a case-by case basis)
- Impact of vomiting after oral administration but before 2x of median  $t_{max}$  (e.g. excluding the participant) will be assessed on a case-to-case basis for the impact on the overall result.
- Sample processing errors that may lead to inaccurate bioanalytical results
- Inaccurate dosing or dosing errors (e.g. dose administration delayed, dose change or missed doses)
- Pre-dose or trough sample collected after the actual dosing
- Non-compliance with food and drink requirements (e.g. non-fasted, incomplete meal consumption, caffeine intake)
- Concomitant medication, vitamins, dietary or herbal supplements

Should one or more of these events be available at the Data Review Meeting, its implication for PK evaluation will be discussed and agreed amongst relevant study team members (e.g. Sponsor Clinical Pharmacology/Biostatistics/Clinical Pharmacokinetics & Pharmacodynamics team representative). Appropriate action will be taken such as flagging individual values to be excluded from analysis.

The protocol deviations recorded in the Clinical Trial Management System (CTMS) may utilize different terminology. The table below displays how the terminology used in CTMS translates to the terminology used in the IAP, the SDTM and ADaM datasets, and ultimately the CSR:

CTMS	IAP	SDTM	ADaM
Non-important	Non-important (only for protocol deviations related to COVID-19)	Only protocol deviations related to COVID-19 are included	Only protocol deviations related to COVID-19 are included
Important	Important	Flagged with PDEVXXX code	Flagged with PDEVXXX code
Clinically Important	Clinically important	Mapped to Important	Mapped to Important

A full list of potential protocol deviations including definition and categorization is maintained by PPD in the “Study Specific Protocol Deviation List” attached to the Protocol Deviation Management Plan.

A frequency table as well as a listing of important protocol deviations, will be provided based on the FAS/SAF.

Referring to FDA, a listing of all participants affected by the COVID-19 related study disruption will be produced by unique subject number identifier and by investigational site, and a description of how the individual’s participation was altered for the Part 1A and Part 1B.

### **10.2.2 Reasons Leading to the Exclusion from an Analysis Set**

A frequency table organized according to reason for exclusion from the DLT analysis set, as well as a listing, will be provided. More details can be found in Section 8.1.

## **11 Demographics and Other Baseline Characteristics**

Demographic data and other baseline characteristics will be presented for the FAS/SAF analysis set using summary statistics for continuous variables and frequency statistics (i.e. counts and percentages) for categorical variables. Results will be presented as indicated in Section 9.

Listings showing demographic data and other baseline characteristics will be presented for the FAS.

### **11.1 Demographics**

Demographic characteristics and physical measurements will be summarized descriptively using the following information from the Screening Visit eCRF pages.

The following demographic characteristics will be included:

- Sex: male, female
- Race: White, Black or African American, Asian, American Indian or Alaska Native, Native Hawaiian or Other Pacific Islander, More than one race, Not collected at this site, Other
- Ethnic origin: Hispanic or Latino/Not Hispanic or Latino
- Age (years)
- Age categories: < 65 years, ≥ 65 years
- Pooled Region: North America
- Weight (kg) at Baseline
- BMI (kg/m^2) at Baseline
- Eastern Cooperative Oncology Group (ECOG) Performance status (0,1,2,3,4)
- Tobacco use status (former/current/never)

Specifications for computation:

Age [years]

- Date of birth is: (date of given informed consent - date of birth + 1) / 365.25
- In case of missing day for at least one date, but month and year available for both dates:
- For the derivation of age, the day of informed consent and the day of birth will be set to 1 and the formula above will be used
- In case of missing month for at least one date, but year available for both dates:
- For the derivation of age, the day and the month of informed consent and the day and month of birth will be set to 1 and the formula above will be used
- The integer part of the calculated age will be used for reporting purposes.

Specifications for computation:

$$\text{BMI } [\text{kg}/\text{m}^2] = \frac{\text{weight } [\text{kg}]}{\text{height}[\text{cm}]^2} \times 10000$$

Site codes will be used for the determination of the participant's geographic region.

## 11.2 Medical History

The medical history will be summarized from the "Medical History" eCRF page, using the most recent MedDRA version at time of database lock, preferred term as event category and system organ class (SOC) body term as Body System category. Each participant will be counted only once within each preferred term (PT) or SOC.

Medical history will be displayed in terms of frequency tables: ordered by primary SOC and PT in alphabetical order.

## 11.3 Other Baseline Characteristics

Information on disease characteristics collected at baseline will be summarized and listed. Summary statistics will be presented for:

- ECOG Performance Status
- Site of Primary Tumor by International Classification of Diseases for Oncology (ICD-O)
- Time since initial cancer diagnosis (years) = (date of start of study treatment – date of initial cancer diagnosis + 1) / 365.25
- Time since documented locally advanced, inoperable or metastatic disease diagnosis (years) = (date of start of study treatment – date of documented locally advanced, inoperable or metastatic disease diagnosis + 1) / 365.25
- Tumor histopathologic type: Adenocarcinoma / Squamous cell carcinoma / Other
- Disease stage at initial diagnosis

- Disease stage at study entry

Incomplete dates for initial cancer diagnosis and documented inoperable or metastatic disease diagnosis will be handled as specified in Section [9.8](#).

Baseline characteristics with respect to vital signs, physical examinations, and hematology/biochemistry will be part of Section [15](#) (Safety Evaluation).

## 11.4 Baseline Tumor Assessment

Information collected by the Investigator on the baseline tumor assessment collected at the screening visit on the “Tumor Assessment (according to RECIST 1.1)” eCRF pages and “Sum of Diameters (according to RECIST 1.1)” eCRF page will be presented in a listing.

## 11.5 Prior Anti-cancer Therapy

The prior anti-cancer therapies are collected under the “Prior Anti-Cancer Drug Therapies Details”, “Prior Anti-Cancer Radiotherapy Details” and “Prior Anti-Cancer Surgeries Details”, eCRF pages.

The number and percentage of participants in each of the following anti-cancer therapy categories will be tabulated:

- Participants with at least one type of prior anti-cancer treatment
- Participants with at least one prior anti-cancer drug therapy
- Participants with at least one prior anti-cancer radiotherapy
- Participants with at least one prior anti-cancer surgery

Prior anti-cancer drug therapy will be summarized as follows based on the number and percentage of participants with the following:

- At least one prior anti-cancer drug therapy
- Number of prior anti-cancer therapy regimens: 1 / 2 / 3 /  $\geq 4$
- Prior anti-cancer therapy regimens for metastatic or locally advanced disease
- Type of prior anti-cancer therapy
- Intent of Therapy: Neo-Adjuvant / Adjuvant / Metastatic or Locally advanced
- Best response to last prior treatment: Complete Response (CR) / Partial Response (PR) / Stable Disease (SD) / Progressive Disease (PD) / Not assessable / Unknown / Not applicable. Best response is derived from the last treatment regimen

Listings of prior anti-cancer treatments and procedures will be provided as follows. These will include the participant identification number, and all the relevant collected data fields on the corresponding eCRF pages.

- Listing of prior anti-cancer drug therapies
- Listing of prior anti-cancer radiotherapy
- Listing of prior anti-cancer surgeries

## 12 Previous or Concomitant Therapies/Procedures

The following analyses will be performed based on the FAS/SAF analysis set and presented as indicated in Section 9.

**Concomitant medications** are medications, other than study intervention, which are taken by participants any time during the on-treatment period, see Section 9.7.

**Previous medications** are medications, other than study intervention and pre-medications for study interventions, which started before first administration of study interventions.

A medication may be classified as both concomitant and previous. The respective flags will be derived based on start and end date. To derive these flags in case of missing or partial dates, see Section 9.8.

Concomitant and previous medication each will be summarized by number and percentage of participants from the “Concomitant medications” eCRF. ATC-2nd level (Anatomical Therapeutic Chemical classification class) and PT (Preferred Term) will be summarized as given from the World Health Organization-Drug Dictionary (WHO-DD) most current version.

If any previous or concomitant medication is classified into multiple ATC classes, the medication will be summarized separately under each of these ATC classes.

The summary tables will be sorted by decreasing frequency of drug class and decreasing frequency of preferred term in a given drug class. In case of equal frequency regarding ATC classification level 2 or preferred term, alphabetical order will be used.

In case any specific medication does not have an ATC classification level 2 coded term, it will be summarized under “Unavailable ATC classification” category. Each participant will only be counted once, even if he/she received the same medication at different times.

Any medication recorded on the “Concomitant Medications Details” eCRF page will be listed with an indication of whether the medication was previous, concomitant or both.

All **concomitant procedures**, which were undertaken during the on-treatment period will be summarized according to the CRF page “Concomitant Procedures Details”. Concomitant procedures will be presented according to MedDRA SOC and PT, or in case of analyses of specific interest as classified by medical review. Number and percentage of participants with concurrent procedures (Prior, on or after the first day of study intervention or within 30 days after last dose of study intervention) overall and by type of procedure (as classified by medical review) will be presented.

A listing with the relevant information about concurrent procedures will also be produced. A flag will be added to indicate whether the procedure is:

- Prior: the procedure started before the first dose of study treatment
- Concurrent: as defined above
- Post: the procedure started after the on-treatment period or during the on-treatment period but was still ongoing at the end of it.

A procedure could therefore be prior and concurrent as well as concurrent and post-treatment.

## 13 Study Intervention: Compliance and Exposure

The following analyses will be performed based on the safety analysis set by dose level (and regimen if different regimens are tested) and study part.

All dosing calculations and summaries will be based on “M4076 Administration” eCRFs page.

No imputation of missing start dates of study interventions will be done. In case the last date of study intervention is incomplete the date of last study intervention administration will be taken from the M4076 Termination page.

A dose is regarded as administered if the actual dose received is  $> 0$ .

**Cumulative dose (mg)** is the sum of the actual doses of study intervention received overall.

**Exposure duration (in weeks)** is defined by:

$$\left( \frac{\text{date of last dose of study intervention} - \text{date of first dose of study intervention} + 1}{7} \right)$$

**Dose intensity (mg/3 weeks period)** is defined as:  $\left( \frac{\text{Cumulative dose in mg}}{(\text{Duration (weeks})/3)} \right)$

### Relative Dose Intensity

The relative dose intensity (%) is calculated based on 3-weeks period by dividing the dose intensity by the planned 3-weekly cumulative dose.

The summary of study intervention exposure will include the following information:

- Exposure duration (in weeks): overall distribution and by categories of  $< 1$  period,  $\geq 1$  period to  $< 2$  periods,  $\geq 2$  period to  $< 3$  periods, and  $\geq 3$  periods. Categories may be updated based on observed treatment duration. Counts of participants who discontinued during each period (Period 1, Period 2, Period  $\geq 3$ ) will be provided along with reason for treatment discontinuation.
- Cumulative dose (mg): overall distribution
- Dose intensity (mg/3 week): overall distribution

- Relative dose intensity (%) by categories of < 60%,  $\geq 60\%$  to < 80%,  $\geq 80\%$  to < 90%,  $\geq 90\%$  to  $\leq 120\%$ , and  $> 120\%$
- Number and percentage of participants with at least one dose reduction (overall and by primary reason):
  - Due to adverse event
  - Due to other reason
- Number and percentage of participants with at least one missed dose (overall and by primary reason):
  - Due to adverse event
  - Due to other reason
- Number of missed doses per cycles (Cycle 1, Cycle 2, Cycle  $\geq 3$ ) by categories of: 1 to 4 missed doses; 5 to 10 missed doses;  $\geq 11$  missed doses.

Note: Cycles are calculated as treatment periods of 3 weeks (21 days) in length.

A listing will be provided for all study intervention administrations. In Part B1, information on meal intake will be provided in addition to the study intervention administration details.

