Vital Signs	X	X					X				Vital signs are to be measured as follows: 
Day -7 and Day 1, at predose (within approximately 30 to 60 minutes prior) and

Assessment and Procedures	Screen	Food Effect Assessment									Treatment	Notes
Day	D-28 to -8	-7	-6	-5	-4	-3 to -1	1	2	3	4		
Visit Window (days)							-1					Day 1 assessments that could be completed on Day -1 are limited to physical examination, height/weight, and ECOG performance status.
												• 4 hours (\pm 1 hour) postdose
Serum Chemistry	X	X					X					See Appendix 6 for details.
Hematology and Coagulation (PT, aPTT, INR)	X	X					X					See Appendix 6 for details.
Urinalysis	X	X					X					See Appendix 6 for details.
Standard 12-lead ECG	X											
TriPLICATE digital ECG		X					X					ECG should only be collected for participants dosed in the fasted state. See Table 4 for triPLICATE ECG details.
AE and SAE assessment	Continuous											
Concomitant medications and procedures review												

Assessment and Procedures	Screen	Food Effect Assessment								Treatment	Notes
Day	D-28 to -8	-7	-6	-5	-4	-3 to -1	1	2	3	4	
Visit Window (days)							-1				Day 1 assessments that could be completed on Day -1 are limited to physical examination, height/weight, and ECOG performance status.
Study Intervention and Treatment											
Low-fat Meal or Overnight Fasting (Fasting window: 10 hours predose to 4 hours postdose)		X	X				X				Participants in Part 1B will be randomly assigned on a 1:1 basis to 1 of 2 study intervention sequences: (1) fasted followed by fed, or (2) fed followed by fasted. After completion of food effect assessments, participants may continue to receive study intervention at RDE from D4 onward (on an empty stomach) and follow assessments as per Table 1 from D8 onwards.
M4076 Administration (single dose)		X					X			X	After D4, M4076 dosing should continue at the RDE and thereafter follow assessments as per Table 1 .
Pharmacokinetic Assessments:											
Blood – PK blood samples M4076		X	X	X	X		X	X	X	X	See Table 4 for PK sample details.
Urine PK Collection		X	X	X	X		X	X	X	X	See Table 4 for urine PK sample details.
CCI											

Assessment and Procedures	Screen	Food Effect Assessment								Treatment	Notes
Day	D-28 to -8	-7	-6	-5	-4	-3 to -1	1	2	3	4	
Visit Window (days)							-1				Day 1 assessments that could be completed on Day -1 are limited to physical examination, height/weight, and ECOG performance status.
CCI											

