4.1.2 Part 1B – Preliminary Food Effect Assessment

Part 1B may begin enrolling once the MTD or RDE is defined in Part 1A and will follow a randomized, 2-sequence, 2-period, cross-over design with a target sample size of 12 participants. Participants will be randomized by the Interactive (phone and web) Response System (IXRS) to 1 of 2 sequences. Allocation assignment will be done on a 1:1 basis: (1) fasted followed by fed, or (2) fed followed by fasted.

Participants will visit the clinic from Day -7 to Day -4 during which they will receive a single M4076 dose with PK samples collected as outlined in [Table 2](#). Participants will receive another dose on Day 1 to ensure an approximate one-week washout period between administrations. Once the PK of M4076 is characterized, the minimum washout period may be changed to 5 half-lives at the discretion of the Sponsor, if warranted. The fed meal condition is planned to be a standard low-fat meal (see [Appendix 8](#)). PK samples will be collected for both fed and fasted study interventions. Triplicate ECG samples will be collected only for participants dosed in the fasted state (see Section 6.1 for details regarding the fasting window). Additionally, if the half-life of M4076 is substantially longer than originally predicted, the PK sampling timepoints after the first dose on Day -7 may be adjusted, as described in the Schedule of Activities (Section [1.3.2](#)).

The SMC will continue to monitor the safety of M4076 and may recommend continuing at the same dose, change the dose (not higher than MTD defined in Part 1A), or stop Part 1B.

Unacceptable toxicity for Part 1B will be AEs that fulfill the DLT criteria (as defined in Section 6.6) regardless of when they occur during treatment. Adverse events will be collected and reported in similar manner to Part 1A of the study. The SMC decisions in Part 1B will also be supported by a Bayesian Model. Refer to Section 9.4.4 for details.

The Pd of M4076 will also be investigated in Part 1B. Paired tumor biopsies and serial peripheral blood mononuclear cells samples will be collected to evaluate markers of ATM activation and inhibition, as well as of DNA damage. The collection of paired tumor biopsies is mandatory, unless contraindicated for medical reasons. If insufficient paired tumor biopsies are obtained, additional participants consenting to provide paired tumor biopsies may be added at the discretion of the Sponsor.

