## 9.7 Exposure time

**Duration of exposure to study intervention** = date of last dose of study intervention – date of first dose of study intervention +1.

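### In Part 1B no fixed 3-weekly planned dose makes the SAP's relative dose intensity read 100% for full compliance, so the denominator must follow the schedule

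*SAP*

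**What the plan says.** SAP Section 13 runs the compliance and exposure analyses "by dose level (and regimen if different regimens are tested) and study part", so one set of formulas serves Parts 1A and 1B.

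- Cumulative dose "is the sum of the actual doses of study intervention received overall".
- Exposure duration, in SAP 9.7 and again (in weeks) in SAP 13, is "date of last dose of study intervention – date of first dose of study intervention +1". Nothing is deducted for days on which no dose is planned.
- Dose intensity is the cumulative dose divided by the number of 3-week periods in that duration.
- RDI comes from "dividing the dose intensity by the planned 3-weekly cumulative dose". It is reported in five bands: below 60%, 60 to below 80%, 80 to below 90%, 90 to 120%, and above 120%. The planned term is not defined for Part 1B.

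Protocol 4.1.2 sets the Part 1B schedule: "Participants will visit the clinic from Day -7 to Day -4 during which they will receive a single M4076 dose", and then "Participants will receive another dose on Day 1 to ensure an approximate one-week washout period between administrations". Table 2 in protocol 1.3.2 places the start of continuous dosing on Day 4: "participants may continue to receive study intervention at RDE from D4 onward (on an empty stomach". Protocol 1.3.2 also lets the washout be changed once the PK is known, to between 1 and 6 days.

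SAP 9.3 has no Day 0. For Part 1B it names Day 1 as the day on which study intervention starts, although the first dose is given on Day -7.

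**The concern.** The duration term counts every calendar day from Day -7, while the numerator gains nothing on the days left free of dosing by design. In Part 1A, with daily dosing, the two stay in step and full compliance gives 100%. In Part 1B they do not. A participant who took every planned dose could be reported in a band that suggests under-dosing or, under another reading of the planned term, over-dosing. Part 1B is planned at the recommended dose for expansion or lower, so an artefact in this table could be misread as a signal about tolerability or adherence at that dose. The Part 1A and Part 1B columns would also not be comparable.

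**Working it through.** **Inputs.** T is the number of days from first to last dose, inclusive (SAP 9.7 and 13). D is the daily dose, assumed equal for the two single doses and for continuous dosing. Doses are planned on Day -7, Day 1, and daily from Day 4 (protocol 4.1.2 and Table 2). Without a Day 0, Day -7 to Day 3 is 10 calendar days with 2 doses. That leaves 8 planned no-dose days: Days -6 to -1, and Days 2 and 3. The schedule labels only Days -3 to -1 as washout, but all 8 days drive the result. The plan states no RDI figure to reproduce.

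**Formula.** RDI = [cumulative dose / (T/21)] / P, where P is the planned 3-weekly cumulative dose.

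**Check on Part 1A.** Cumulative dose = T × D and P = 21D, so RDI = (TD × 21/T)/(21D) = 100% for every T.

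**Part 1B, full compliance, T of 11 or more.** Doses taken = 2 + (T − 10) = T − 8. Dose intensity = 21D(T − 8)/T, which rises steadily with T. A constant P can equal it at one value of T at most.

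**P = 21 daily doses.** RDI = (T − 8)/T.

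| T (days) | Doses taken | RDI | Band |
|---|---|---|---|
| 21 | 13 | 13/21 = 61.9% | 60 to below 80% |
| 42 | 34 | 34/42 = 81.0% | 80 to below 90% |
| 63 | 55 | 55/63 = 87.3% | 80 to below 90% |
| 80 | 72 | 72/80 = 90.0% | 90 to 120% |
| 105 | 97 | 97/105 = 92.4% | 90 to 120% |

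RDI is below 60% for T under 20 and below 80% for T under 40. It never reaches 100%.

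**Same P, washout shortened to 1 day** (taken as one dose-free day between the two single doses). The no-dose days fall to 1 + 2 = 3, so RDI = (T − 3)/T: 18/21 = 85.7% at T = 21, 39/42 = 92.9% at T = 42, and 27/30 = 90.0% at T = 30.

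**P = the 13 doses scheduled in the first 21 days of Part 1B.** RDI = 21(T − 8)/(13T): 100% at T = 21, 121.2% at T = 32 (the first day above 120%), and 21 × 34/(13 × 42) = 130.8% at T = 42.

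**Duration counted from Day 1, following SAP 9.3, with P = 21 daily doses.** At 21 days, 19/21 = 90.5%, or 20/21 = 95.2% if the Day -7 dose stays in the numerator.

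**P matched to the schedule over the same window.** RDI = (T − 8)D/[(T − 8)D] = 100% for every T. Starting both terms at Day 4 also gives 100%.

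**The case against.** The strongest reply is that the SAP does not define the planned 3-weekly dose for Part 1B. It nowhere says that planned no-dose days count as daily-dosing days, and because results are given by study part, a part-specific planned dose would fit the wording. On that view this is a missing definition and not an error. Part of this stands: the direction of the bias depends on the undefined term, and a reader who infers that the SAP counts the washout as daily dosing goes further than the text. It does not rescue the formula, because a per-3-week constant fails whichever value is chosen. Only a quantity that follows the participant's own schedule works, and the SAP does not specify one for RDI. For actual-dose assignment (SAP 9) it does measure compliance against what the participant was due to receive.

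Two further inferences are tempting and are not supported:

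- *Planned no-dose days will appear as missed doses in Cycle 1.* The SAP gives no rule that derives missed doses from calendar days. It tabulates them by reason, and dosing summaries come from the administration eCRF page. A day without a prescribed dose is not ordinarily a missed dose.
- *Most compliant participants will fall below 90%.* This needs Part 1B treatment durations, which the documents do not give. The only figure is about 105 days on study, not split into phases. If all of it were treatment, RDI would be 92.4%. If it included 28 days of screening and 30 days of follow-up (an assumption), 47 days would remain and RDI would be 39/47 = 83.0%.

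It is also fair that the remaining exposure outputs (cumulative dose, duration, dose reductions, the listing of every administration) let a careful reader see what happened.

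**Conclusion.** The point holds for the RDI formula in Part 1B. With any fixed 3-weekly denominator, a fully compliant participant is misstated at all but at most one exposure length. With 21 daily doses and the planned interval, RDI is too low at every exposure length and below the 90% band until day 80. With a 1-day washout it is below that band until day 30. With the 13-dose denominator it exceeds 120% from day 32. These figures assume full compliance, one dose level throughout, and duration counted from Day -7.

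The consequence is limited. RDI is a descriptive summary in about 12 participants, in a part of the study that may not take place, and no decision rule uses it. DLT evaluability, actual-dose assignment and the food-effect model do not depend on it. It is worth correcting because the table would otherwise misdescribe compliant participants and correction costs almost nothing.

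**What to change.** Add to SAP Section 13, for Part 1B, one of the following:

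1. RDI is the actual cumulative dose divided by the protocol-planned cumulative dose over the participant's own exposure window (the two single doses plus daily dosing from Day 4, using the washout actually scheduled); or
2. RDI is computed from Day 4 onward, with the two food-effect doses listed separately.

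Either gives 100% under full compliance. In the same edit, state that days without a planned dose are not missed doses. This is a clarification for the programmer, since the SAP does not say otherwise. Also reconcile the SAP 9.3 statement that intervention starts on Day 1 with the first Part 1B dose on Day -7, so that the start of exposure is unambiguous.

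The cost is a sentence or two in the SAP and a small programming rule. No new data are needed, and no other analysis changes.
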